5. STUDY INTERVENTIONS

5.1. INTERVENTIONS, ADMINISTRATION, AND DURATION

Participants will be randomized to either candesartan or placebo in a 1:1 fashion. All participants will be initiated on 8 mg. The dose will be increased in 2 week increments to 16 mg and 32 mg as long as: SBP>110 mm Hg, DBP>40 mm Hg and participant reports no symptoms of hypotension (dizziness or weakness). The highest achievable dose will be the Maximal Tolerated Dose (MDT) and will be prescribed for the duration of the study. The cut-off of 110 mm Hg for SBP is based on the evidence that a decrease of ≤5 mm Hg in SBP is expected in non-hypertensive individuals. Hence, a cutoff of 110 mm Hg in SBP decreases the risk of developing hypotension (defined as <100 mm Hg in SBP). Treatment will be provided in similar capsules format to be taken once a day orally. Investigators, study personnel and participants will be blinded for drug assignment. Participants will be treated for 1 year.

5.2. HANDLING OF STUDY INTERVENTIONS

The drugs will be stored in the medication room in the Investigational Drug Service (IDS) Pharmacy. The location of the IDS pharmacy is The Emory Clinic [name]. Access to the med room is limited to the IDS Pharmacists via a badge swipe. Accountability records are maintained for all investigational product (IP). A courier will deliver prescriptions to study location to be given to subjects or study staff will be able to pick up prescriptions.

5.3. CONCOMITANT INTERVENTION

5.3.1. ALLOWED INTERVENTIONS

Participants will continue to receive their usual care from their regular primary care physicians. In the event a participant becomes hypertensive during the trial, the participant will be referred to the primary care provider for further hypertension management. Participants will be allowed to use any class of antihypertensive medication except another ARB, an ACEI, or a renin inhibitor. The PMD will be notified of the potential that the subject might be receiving candesartan to avoid this overlap.

5.3.2. PROHIBITED INTERVENTIONS

Additions of an ARB, ACEI, or renin inhibitors are prohibited during the study period. Participating in another clinical trial or study is prohibited.

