Our target population includes subjects who are 50 years or older who are not receiving antihypertensive medications with MCI and AD. Our sample size is 72 for this trial. All 72 subjects will be invited to participate in the additional PET study.

SCHEDULE OF PROCEDURES FOR THE DURTAION OF THE STUDY

Phase:	SCREEN	BASELINE		TITRATION		FOL	LOW	-UP
Number of visits	1-2	1-3		2			4	
Months	-1	0		1-2	3	6	9	12
Informed Consent	Х							
Cognitive screening	Х							
Screening labs	X*							
Amyloid Positivity to assess eligibility	X**							
CSF for molecular analysis	X***	X***						Х
Weight/Height		Х		Х	Х	Х	Х	Х
Blood Pressure	Х	Х	NOI	Х	Х	Х	Х	Х
Safety labs			IZAT	X#	X#	Χ^	X#	Χ^
Brain MRI		Х	MO					Х
In-vivo A β and Tau PET scan	X**	X**	AND					Х
Vascular function measures		Х	R					Х
Cognitive Battery		Х				Х		Х
Functional battery (IADL, SPPB)		Х						Х
RAS biomarkers (blood and CSF)		Х				Х		Х
APOE genotype		Х						
Retinal scan and blood draw****								
Inflammatory/molecular biomarkers (proteomics /metabolomics)	X\$	X\$						X
Time (in minutes)	60-120	150-210		30	30	75	30	150-210

*: Screening labs include: CBC, CMP (BUN, CR, electrolytes, liver function), B12, TSH and PT/INR

**: Amyloid positivity can be assessed by either LP (CSF levels of amyloid) or PIB-PET. We will routinely use LP as the default method to determine Amyloid positivity however, in some instances e.g. a failed LP or delayed CSF results due to lab issues then we will use a screening PIB-PET instead. If a PIB-PET was done at screening, it WILL NOT be repeated at baseline. Subjects will only have Tau-Pet at baseline.

***: If subject has had an LP within the 6 months prior to their screening/baseline visit and samples are available for assessing eligibility and for measuring CSF outcomes then no LP will be done at screening. If CSF is only available for eligibility assessment (e.g. from PIB-PET/ clinical LP/assessment/ another research study and subject willing to share these samples) then an LP will be done to obtain CSF for the outcome measures (such as molecular analysis). This LP can be done at baseline instead of screening (since eligibility would have been already established).

****: Retinal scan +/- 10 cc blood draw are optional and can be done at any visit or after the completion of the study.

#: Safety labs at titration, 3 and 9 months include BMP (BUN, CR, electrolytes)

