^: Safety labs at 6 months and 12 months include BMP (BUN, CR, electrolytes) + CBC. If subject started taking any blood thinners during the study, PT/INR will be repeated before LP at 12 months.

\$: Samples for inflammatory/molecular biomarkers will be drawn either at screening or at baseline visits.

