4.2. EXCLUSION CRITERIA

(1) Intolerance to ARBs;

(2) Current use of ARBs or ACEI (use of antihypertensive medications other than ACEI or ARBs for other indications is allowed);

(3) Current diagnosis of hypertension or current use of antihypertensive medication that is prescribed specifically for hypertensive therapy;

(4) SBP less than 110 or DBP less than 40 mm Hg;

(5) Renal disease (Creatinine >2.0 mg/dl), hyperkalemia (K>5.5 meq/dl), platelets<50,000/μl, or INR>1.9;

(6) Active medical or psychiatric diseases that in the judgment of the investigator would affect the safety of the subject or scientific integrity of the study e.g. if the patient has hypothyroidism or low vitamin B12 that is contributing to the subject's cognitive impairment;

(7) Uncontrolled congestive heart failure reflected by poor exercise tolerance and shortness of breath;

(8) History of stroke in the past 3 years;

(9) Inability to have MRI (eg metal implants or cardiac pacemaker) with an exception for those who cannot have an MRI, if all other parts of the study are obtained successfully they may still be enrolled in the study, or cognitive assessment or inability to assess amyloid positivity (no LP and no amyloid scan);

(10) History of increased intracranial pressure (ICP) or bleeding diathesis (from disease states or from use of anticoagulants such as warfarin, heparin and related products, Rivaroxaban or Xarelto, Apixaban or Eliquis, Edoxaban or Savaysa, Dabigatraban or Pradaxa);

(11) Women of childbearing potential (non-menopausal);

(12) In those who are unable to demonstrate that they understood the details of the study (ie lack of decisionalcapacity to consent), a study partner/surrogate who can sign on their behalf will be required, otherwise they will be excluded;

(13) Current use of Lithium, as Candesartan may increase lithium concentration to toxic levels.

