6. STUDY PROCEDURES AND MEASURES

6.1. QUESTIONNAIRES, LIFESTYLE AND ANTHROPOMETRIC MEASURES

Study interviews will be conducted in English and include the following:

(1) Demographic, social, stress, physical activity data and medical history data, as well as a medication inventory will be collected. All participants are asked to bring all their prescribed medication bottles.

(2) Instrumental activities of daily living (IADL) scale .⁵²

(3) Weight and height (stadiometer to measure height with the subjects standing and balance beam scale to measure weight without shoes).

(4) Short Physical Performance Battery [SPPB: ability to stand with the feet side-by-side, semi-tandem, and tandem, time to walk 8 feet (measured twice), and time to rise from a chair and return to the seated position 5 times).⁵³

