7.4. FOLLOW-UP FOR ADVERSE EVENTS

All AE/SAE's will be recorded in the participant chart with start/stop date. The study physician may perform additional evaluations, visits, phone communication, repeat blood testing, or refer to the emergency room or the participant healthcare provider for medical care if necessary. If the event results in intervention discontinuation and/or study withdrawal, the participant will be followed for 2 months post-withdrawal with a monthly phone call. They will also be invited to perform the final visit evaluation including all study procedures planned for that visit if the participant has been in the study more than 5 month post baseline evaluation.

Follow-up on reported symptoms of hypotension or a BP<100/40 mm Hq: When a subject notifies the study team that they have either symptoms suggestive of hypotension (dizziness, weakness, near syncope, or syncope) or that their blood pressure is less than 100/40 mm Hg, the study physician will review the incident and determine if the subject is safe to continue in the study. The physician may discontinue the study medication immediately, elect to lower the dose of the study medication, ask subject to present to the study center for a safety evaluation, and/or monitor the subject blood pressure. The subject may continue in the study if blood pressure is >100/40 mm Hg on the lower dose of the study medication and had resolution of symptoms. In those on 16 mg and 32 mg, the doses will be decreased to the next lower dose. Those on 8 mg of candesartan, a trial of every other day 8 mg of candesartan will be attempted prior to discontinuation.

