8. INTERVENTION DISCONTINUATION

A subject may choose to withdraw from the study for any reason. The investigators may also request that the subject withdraw from the study, for safety or other reasons. The criteria for discontinuing a subject's participation include:

(1) the subject's request,

(2) adverse events that requires un-blinding or necessitate stopping the study drugs,

(3) persistent (>2 episodes on 2 separate days) of symptomatic hypotension or a blood pressure <100/40 mm Hg on 2 separate occasions despite adjusting study medication to the lowest dose (see section on follow-up on AE 7.4).(4) new clinically evident stroke or myocardial infarction or other event that limits ability to complete the study procedures

(4) inability to participate due to relocation or other personal reasons,

(5) renal failure (increase in serum Creatinine above 2.5 mg/dl) or hyperkalemia (greater than 5.9 meq)

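### Lithium is excluded at entry because of an interaction with candesartan, but section 5.3.2 does not list it among the additions prohibited on treatment.

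*Combined protocol and SAP*

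**What the plan says.** Lithium appears once, in the last exclusion criterion of section 4.2: "Current use of Lithium, as Candesartan may increase lithium concentration to toxic levels". The criterion concerns use at the time of enrolment.

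The on-treatment rule is in section 5.3.2: "Additions of an ARB, ACEI, or renin inhibitors are prohibited during the study period". Its second sentence bars joining another study. Section 5.3.1 states "Participants will continue to receive their usual care from their regular primary care physicians". It also provides for telling the participant's physician that candesartan may be in use, so that overlap with the drug classes named there is avoided. Section 11.3 makes contact with the primary care physician conditional on the participant's agreement.

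Several general safeguards exist:

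- Section 6.1 provides for a medication inventory: "All participants are asked to bring all their prescribed medication bottles".
- The footnotes to the Schedule of Procedures set the laboratory checks: "Safety labs at titration, 3 and 9 months include BMP (BUN, CR, electrolytes)" and "Safety labs at 6 months and 12 months include BMP (BUN, CR, electrolytes) + CBC". No lithium level is listed.
- Section 7.4 lets the study physician add visits or blood tests after an adverse event.
- Section 8 lists reasons for discontinuation, including "adverse events that requires un-blinding or necessitate stopping the study drugs", creatinine above 2.5 mg/dl and potassium above 5.9. It also lets the investigators ask a participant to withdraw on safety grounds.

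**The concern.** The protocol's own reason for the lithium exclusion is a drug interaction. A person not taking candesartan is not exposed to it, so the period that needs a rule is the year of treatment. The written rule covers only the moment of entry.

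What is at stake is the safety of a participant on candesartan whose own doctor starts lithium. That doctor may not know of the risk, because the notice in 5.3.1 is about overlapping renin-angiotensin drugs. Site staff who check a new prescription against 5.3.2 would find nothing to act on.

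**Working it through.** The plan gives no figure to reproduce. The check is mainly a comparison of rules.

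**Step 1: do entry exclusions carry over to treatment?** No sentence says so, and three comparisons within the protocol suggest that they do not carry over by default.

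| Drug group | At entry (4.2) | On treatment |
|---|---|---|
| ARB, ACEI | Excluded, criterion 2 | Banned again in 5.3.2 |
| Antihypertensives prescribed for hypertension | Excluded, criterion 3 | Allowed by 5.3.1 if hypertension develops, except ARB, ACEI and renin inhibitors |
| Anticoagulants, as a cause of bleeding diathesis | Excluded, criterion 10 | Blood-thinner starts are foreseen: PT/INR is repeated before the month-12 lumbar puncture (schedule footnote) |
| Lithium | Excluded, criterion 13 | Not mentioned |

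Where an exclusion is meant to bind on treatment, the plan restates it. Where it is relaxed or managed, the plan says so. Lithium gets neither.

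**Step 2: would another provision be triggered by a lithium start?**

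- The inventory in 6.1 could reveal it. However, 6.1 does not say how often the inventory is repeated, the schedule has no row for it, and no action is attached.
- The BMP could show renal or electrolyte change, but not a lithium level.
- The section 8 thresholds and its adverse-event criterion need harm to have appeared. The general power to request withdrawal does not, but its use is discretionary.
- Visits after titration are three months apart with a window of three weeks either side (6.12.2). Taking three months as 13 weeks, the longest gap between consecutive visits is 13 + 3 + 3 = 19 weeks.

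**Step 3: size.** The documents give no rate of new lithium use, so the number of starts is an assumption.

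- Candesartan arm at 1:1: 72 / 2 = 36.
- Expected starts on candesartan = starts × 36/72. With 0 to 1 starts, this is 0 to 0.5. With 2 starts, it is 1.0.
- One participant is 1/72 = 1.4% of the sample.
- Visits after randomisation at which the inventory could be reviewed: 2 titration + 4 follow-up = 6, so at most 72 × 6 = 432 reviews.

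**The case against.** The strongest reply is that the plan already has the means to act. Criterion 13 puts the investigators on notice of the hazard. Section 8 lets them request withdrawal on safety grounds before any harm occurs. The inventory and the repeated chemistry make discovery possible. Entry also removes current lithium users and, under criterion 6, people whose active psychiatric disease would in the investigator's judgment affect safety. New starts should therefore be very rare. All of this stands, and it keeps the point minor. What it leaves open is an explicit rule, a set check and a defined response.

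A reader might infer that the plan permits candesartan with lithium. The documents do not support that. Silence in 5.3.2 is not permission, the usual-care sentence in 5.3.1 is general, and the only drugs 5.3.1 expressly allows are certain antihypertensives. A reader might also infer that participants have no protection at all, which section 8 contradicts.

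The consent form is not in the text reviewed. It may carry lithium advice for participants, which could not be checked. Such advice would help in practice but would not change 5.3.2.

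**Conclusion.** The gap is real and minor. A hazard that the protocol names, and that exists only on treatment, is covered by an entry rule and is missing from the on-treatment list. Confidence is high on the text. The practical consequence is uncertain and probably very small: 0 to 0.5 expected participants on candesartan if 0 to 1 of the 72 start lithium, an assumed range.

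The point is confined to patient safety. It gives no ground for doubting the endpoints, sample size or analysis. Nor do the documents show that a lithium start must always end study treatment. Stopping study drug and monitoring lithium levels are both defensible policies, and the plan should state which applies.

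**What to change.** 1. Add lithium to the prohibited additions in 5.3.2.
2. Add lithium to the physician notice in 5.3.1, sent where the participant agrees (11.3). That notice sits beside the text on participants who become hypertensive, so the amended sentence should say when it is sent.
3. Specify that the existing medication inventory is reviewed for lithium at each titration and follow-up visit, including visits held by phone.
4. State the response: if lithium is started or judged necessary, the study physician reviews promptly and holds study drug unless the prescriber is monitoring lithium levels. Scheduled follow-up continues, including month 12, for the intention-to-treat analysis. This needs stating because the provision in 7.4 that "the participant will be followed for 2 months post-withdrawal with a monthly phone call" applies to stops caused by an adverse event, and a lithium start is not one.

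The cost is a few sentences and at most 432 brief inventory reviews at visits already planned, with no new visit, laboratory test or participant. The downside is that, on the assumed 0 to 1 starts, at most about one participant (1.4%) might stop study drug. At 1:1 allocation there is a 50% chance that this participant is on placebo and gains no safety from stopping.

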5.4. ADHERENCE ASSESSMENT

Participants will be asked to bring their study medication bottles to the study center at each visit. Medication compliance will be assessed using pill count during the titration and follow up periods. We will define a compliance rate for a time period, t, as the ratio of: (the used number of pill prescribed for the number of days t - number of pills remaining or unused for the time t / number of pills prescribed for time t) multiplied by 100.

6. STUDY PROCEDURES AND MEASURES

6.1. QUESTIONNAIRES, LIFESTYLE AND ANTHROPOMETRIC MEASURES

Study interviews will be conducted in English and include the following:

(1) Demographic, social, stress, physical activity data and medical history data, as well as a medication inventory will be collected. All participants are asked to bring all their prescribed medication bottles.

(2) Instrumental activities of daily living (IADL) scale .⁵²

(3) Weight and height (stadiometer to measure height with the subjects standing and balance beam scale to measure weight without shoes).

(4) Short Physical Performance Battery [SPPB: ability to stand with the feet side-by-side, semi-tandem, and tandem, time to walk 8 feet (measured twice), and time to rise from a chair and return to the seated position 5 times).⁵³

6.2. BLOOD PRESSURE MEASUREMENT

Office blood pressure will be measured according to the American Heart Association guidelines: sitting position, rested for 5 minutes, appropriate cuff size (covering 60% of upper arm length and 80% of arm circumference), correct cuff placement (1-2 inches above brachial pulse on bare arm). Measurement will be done manually using the bell of the stethoscope or using a validated and calibrated automatic machine. Blood pressure will be measured in both arms. The arm with the higher blood pressure will be used throughout the study. We will obtain 2 seated readings followed by 2 standing blood pressure measurements at 1 and 3 minutes during each visit.

6.3. NEUROPSYCHOLOGICAL ASSESSMENT:

(i) *Clinical Dementia Rating- (CDR)*. The CDR rates each of the six general domains (or boxes) involving memory, orientation, judgment and problem-solving, community affairs, home and hobbies, and personal care, and a global rating is then generated, ranging from 0-no impairment to 3-severe impairment. A Study informant or study partner will be questioned either by phone or in person to assist with the CDR.

(ii) EXecutive Abilities Measures and Instruments for Neurobehavioral Evaluation and Research or "EXAMINER"⁵⁴: This is a test battery that reliably and validly assesses executive function in clinical trials: working memory, inhibition, set shifting, and fluency. The EXAMINER battery has excellent psychometric properties with test-retest reliability of over 0.9 and correlates by over 0.60 with an informant-based measure of day-to-day executive functioning, the Frontal Systems Behavior Scale. The parts of EXAMINER that we selected include:

1) Flanker task (inhibition) which involves responding to a central stimulus while ignoring flanking stimuli that are either compatible or incompatible with the central stimulus.⁵⁵

2) Set-shifting, a measure of mental flexibility assessing the subject's ability to attend to the specific attributes of compound stimuli, and to shift that attention when required.⁵⁶

3) Spatial 1-Back test assesses spatial working memory and

4) Dot Counting test assesses verbal working memory.⁵⁷

5) Verbal Fluency will be tested using a List Generation test which require the participant to generate words beginning with a specific letter, and category fluency in which the participant generates words from a specified category (e.g., animals, fruits).⁵⁸

(iii) To assess additional cognitive domains/mood, we will use these tests included in the National Alzheimer's Coordinating Center Uniform Data Set.^{59,60}

1) Hopkins Verbal Learning Test will be used to assess memory domains.⁶¹

2) Digit Span Test (DST) is a brief task that assesses attention.^{62,63}

3) Boston Naming Test assesses language by measuring ability of naming a visual confrontation drawing (15 items).^{64,65}

4) Trail Making Test: will be used as an additional measure of executive function.

5) Center for Epidemiologic Studies Depression Scale (CESD),⁶⁶ and consists of 20 items, each scored from 0 to 3 points and higher scores indicate greater depressive symptoms.

(iv) Voice recording to assess speech changes related to cognitive function may be collected at one or more visits. These will include a recording of the cognitive tests, free speech, speech in response to questions, and speech in response to specific cognitive tasks such as counting, fluency and/or a picture description. All voice recording files will not contain personal identifiers or PHI. They will be saved under the subject deidentified study number.

6.4. CEREBROSPINAL FLUID (CSF) COLLECTION

Participant will have CSF acquired via lumbar puncture (LP). In some instances, subjects would have had an LP as part of clinical evaluations or other research studies. If we are able to determine eligibility from the prior LP (within 6 months of the screening visit) and samples are available for the molecular analysis, then screening LP will not be necessary. Otherwise an LP will be done at screening. All CSF samples will be collected after at least 6-hour fast from the last meal. CSF will be collected using a 24-g Sprotte atraumatic spinal needles. This needle decreases the frequency of post LP headaches to < 1%.⁶⁷ All CSF collection is completed according to guidelines put forth in the "Biospecimens Best Practice Guidelines for the ADCs" published by the National Alzheimer's Coordinating Center (NACC) and available on their website. Approximately 30-45 ml of CSF will be collected using sterile polypropylene collection tubes. The samples will be immediately divided into aliquots and transferred for storage in a freezer for future assays. In addition to routine assessment (cells, proteins, albumin, glucose), A β 1-42, t-tau, and p-tau181p will be measured using the multiplex xMAP Luminex platform (Luminex Corp, Austin, TX) with Innogenetics (INNO-BIA AlzBio3; Ghent, Belgium; for research use–only reagents) immunoassay kit–based reagents⁶⁸ at the local ADRC core laboratory.

